### **Data Parameters**

The data parameters listed below will be collected anonymized before being provided to MPO.

### **De-Identified Subject #**

- A minimum of 100 subjects with Evolution NitrX will be assigned a de-identified subject number entered into the case report form.

### **Data Collection and Follow-up Schedule**

Data Collection	3 years	5 years	7 years	10 years
KOOS Jr	X	X	X	X
SAE including Revision	X	X	X	X

## Postoperatively

- Subject Status
  - Is the subject deceased?
  - Date the subject was deceased.
- Is the subject revised?
  - Reasons for revision
  - If a revision occurs, the removed and retained components will be provided.
  - Date that the revision occurred.
- Adverse events
  - Information regarding adverse events that have occurred after surgery will be provided.

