## Synopsis

Study Title	Evolution NitrX Observational Study	
Study Rationale	To evaluate the safety and performance of Evolution NitrX TKA	
Study Design	Single Center observational study	
Study Sites	[name] (PI)	
Sample Size	100	
Visit Schedule	subject schedule will consist of the following time points:	
Study Timeline	3 yr follow up within 2025 5 yr follow up within 2027 7 years follow up 2029 10 years follow up 2032	
Inclusion Criteria	

Subjects > 18 years of age at the time of surgery

Subjects who were implanted with the Evolution NitrX SKU #'s listed below) in MicroPort Orthopedics' intended patient population listed within the Instructions for Use (IFU).

Willing and able to participate in the clinical study

	
Exclusion Criteria	

Subjects without follow-up history

Subjects not meeting the inclusion criteria

Contraindications as listed in the IFU

Currently enrolled in another study that could affect the endpoints of this protocol.

Has a medical or mental health condition, as judged by the investigator, that would affect the endpoints of this protocol.

	
	Objectives	Outcome Measures
Primary	Survivorship (KM)	Kaplan Meier survival rates at each time point
Secondary	PROMS	KOOS Jr
	SAE including Revisions	Track revisions and reason for revisions throughout the study

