## **Data Collection and Parameters**

### **Data Collection Plan**

- 100 cases with min 10-year follow-up, implanted with Evolution NitrX, will be included in this study.
- Data collection will be prospective.
- Patient preop and intra-op information has been collected in study 20K001, and this study is a continuation of that study.
- Information regarding adverse events or revisions after surgery will be obtained from patient charts.
- IRB will be notified of the change in study collection.
- Site will ensure Informed consent does not need to be re-consented and will consult the IRB.
- Subjects will be called or have an office visit,
  - Has undergone index procedure on the operative knee with NitrX and
  - In the 20K001 study and
  - Would be willing to complete a KOOS Jr survey
- Once the survey/questionnaire is completed, the site will compile the data parameters into a data collection form provided by the MPO and send it to the MPO upon completion for analysis.

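### Does the Kaplan-Meier primary outcome fail because no last-confirmed date or lost-to-follow-up status is listed for living, unrevised subjects?

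*Protocol*

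**What the plan says.** The Synopsis gives survivorship as the only primary objective, measured as "Kaplan Meier survival rates at each time point". The Data Collection and Follow-up Schedule puts KOOS Jr and serious adverse events, including revision, at 3, 5, 7 and 10 years.

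The Data Parameters section introduces the list that goes to the sponsor: "The data parameters listed below will be collected anonymized before being provided to MPO". Under Postoperatively, that list asks for:
- vital status ("Is the subject deceased") and the date of death;
- whether the subject is revised, with reason, components and "Date that the revision occurred";
- adverse events.

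The Data Collection Plan describes how the data arise. On contact it says "Subjects will be called or have an office visit". On source it says "Information regarding adverse events or revisions after surgery will be obtained from patient charts". On timing it says "Once the survey/questionnaire is completed, the site will compile the data parameters into a data collection form provided by the MPO". It also states that surgery data come from the preceding study, 20K001, so the time origin is available.

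No section lists a contact date, a date on which implant status was last confirmed, or a lost or withdrawn category.

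**The concern.** A Kaplan-Meier record needs an exit time and an exit state for every subject. The list dates two ways of leaving the risk set, revision and death. It does not date the third, being alive and unrevised when last seen, which probably applies to most of the 100 subjects. An SAP can state a censoring rule but cannot supply a date that nobody recorded.

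Reliance on charts sharpens the worry. A chart with no revision entry looks the same for a subject whose implant is known to be intact and for one who left the practice and may have been revised elsewhere. If silence were read as survival to 10 years, revisions after loss would go unseen, survivorship would be overstated, and the numbers at risk and the standard error would look better than they are.

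**Working it through.** The protocol states no revision rate, loss rate or precision target, so there is no figure of its own to reproduce. The check asks how far the estimate moves under each way of handling unrevised subjects.

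**Inputs.** From the protocol: N = 100, and time points at 3, 5, 7 and 10 years, giving intervals d = 3, 2, 2 and 3 years. Assumed: true 10-year revision of 5%; independent loss at a constant rate reaching L = 20%, 30% or 40% by 10 years.

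- Revision hazard: λ = −ln(0.95)/10 = 0.005129 per year.
- Loss hazard: μ = −ln(1 − L)/10 = 0.02231, 0.03567, 0.05108.
- Sum: s = λ + μ = 0.02744, 0.04080, 0.05621.

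**Standard error with true censoring times** (Greenwood, continuous form): √[0.95² × (λ/100) × (e^(10s) − 1)/s] = 2.31, 2.39, 2.49 points.

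**(a) Data arrive only with a completed survey; censor at the last completed time point.** Among subjects who reach the next time point, the share unrevised over an interval is e^(−λd). The product over the four intervals is e^(−10λ) = 0.95. Estimated revision is 5.0% at every loss rate, so there is no bias.

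**(b) Same censoring, but charts also capture revisions up to the moment of loss.** Lost subjects without a revision go back to their last time point, while revised ones stay in. The interval factor is s/(λe^(sd) + μ). At L = 20% it is 0.98421 for d = 3 and 0.98956 for d = 2, and 0.98421² × 0.98956² = 0.9486. Estimated revision is 5.14%, 5.23%, 5.34%. The largest bias is 0.34 point, and 0.34/2.49 = 0.14 of a standard error.

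**(c) Contacts up to 9 months either side of nominal (assumed), recorded as nominal.** A simulation of 4 million subjects gives 4.88%, 4.87%, 4.92%, against 4.98%, 4.97%, 5.02% with true censoring times in the same samples. The shift is −0.10 point each time.

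**(d) Every lost subject counted as followed to 10 years.** Observed revision is (λ/s)(1 − e^(−10s)).

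| Loss by 10 years | 20% | 30% | 40% |
|---|---|---|---|
| Revision read | 4.49% | 4.21% | 3.92% |
| Apparent SE, √[q(1−q)/100], points | 2.07 | 2.01 | 1.94 |
| SE too small by | 10% | 16% | 22% |
| Apparent at risk at 10 years | 96 | 96 | 96 |
| True at risk, 100e^(−10s) | 76 | 67 | 57 |

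**Sensitivity to the assumed revision rate.** At 40% loss, case (b) gives 2.14% for a true 2% (SE 1.60 points) and 10.65% for a true 10% (SE 3.43 points). The bias is then 0.14/1.60 = 0.09 and 0.65/3.43 = 0.19 of a standard error.

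**Which case does the text support?** The schedule asks for revision status at each time point, so an unrevised answer in a 5-year record is a status at a nominal 5 years. The data are compiled once the survey is complete, so a subject who is not reached has no record for that time point, and the absence itself marks the loss. That is case (a), or case (b) if chart review continues for non-responders. Case (c) may apply on top of either. Nothing in the protocol leads to case (d).

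**The case for a change.** The best argument for a change is that this is a matter of data items and not of analysis. The protocol does set out its parameters, and it omits the one that fixes the risk set. Contact dates not written down at the time may be hard to recover years later. The Data Collection Plan can be read in two ways for subjects who are not reached, and the two readings give different risk sets. The data are meant for regulatory as well as research use, where numbers at risk will be examined. The cost would be two or three fields.

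Part of this stands. The fields are not listed, nominal times are cruder than dates, and a non-responder carries no explicit label. But the two readings are cases (a) and (b), and they differ by at most 0.34 point on the 5% assumption. Numbers at risk can be counted from KOOS Jr completion at each time point. The data collection form that the sponsor provides is not shown, and such forms normally carry a visit date and a disposition field.

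An added field is also not automatically an improvement. If a date of confirmation could come from the chart, a site might enter the day the chart was reviewed instead of the last documented encounter. Lost subjects would then be credited with follow-up they did not have, which is case (d).

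**Conclusion.** The observation is accurate but no change to the plan follows. Read as written, the protocol gives each unrevised subject a nominal censoring time, namely the last time point with a completed survey. On the assumed 5% revision and 20% to 40% loss, the resulting bias in 10-year revision is 0 to 0.3 percentage points. Undated contacts shift the estimate by about 0.1 point in the other direction. The standard error is 2.3 to 2.5 points, so the primary result would be read the same way.

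The sizeable figures (revision understated by up to 1.1 points, standard error up to 22% too small) need an analyst to treat every lost subject as followed to 10 years. The protocol does not prescribe that.

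The conclusion rests on constant hazards, on loss that is independent of revision, and on censoring at the last completed time point. If subjects left because their knee was failing, the estimate would be biased, but a recorded last-contact date would not cure that. What remains is a detail for the data collection form and a censoring rule that can properly sit in an SAP.

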## SCOPE

**Table 1.** Evolution NitrX Scope

Part Number	Product Name
Femoral Components	
EFSAN1PL	EVOLUTION NitrX FEM CS/CR NONPOR TiNbN COATED SZ 1 LEFT
EFSAN2PL	EVOLUTION NitrX FEM CS/CR NONPOR TiNbN COATED SZ 2 LEFT
EFSAN3PL	EVOLUTION NitrX FEM CS/CR NONPOR TiNbN COATED SZ 3 LEFT
EFSAN4PL	EVOLUTION NitrX FEM CS/CR NONPOR TiNbN COATED SZ 4 LEFT
EFSAN5PL	EVOLUTION NitrX FEM CS/CR NONPOR TiNbN COATED SZ 5 LEFT
EFSAN6PL	EVOLUTION NitrX FEM CS/CR NONPOR TiNbN COATED SZ 6 LEFT
EFSAN7PL	EVOLUTION NitrX FEM CS/CR NONPOR TiNbN COATED SZ 7 LEFT
EFSAN8PL	EVOLUTION NitrX FEM CS/CR NONPOR TiNbN COATED SZ 8 LEFT
EFSAN1PR	EVOLUTION NitrX FEM CS/CR NONPOR TiNbN COATED SZ 1 RIGHT
EFSAN2PR	EVOLUTION NitrX FEM CS/CR NONPOR TiNbN COATED SZ 2 RIGHT
EFSAN3PR	EVOLUTION NitrX FEM CS/CR NONPOR TiNbN COATED SZ 3 RIGHT
EFSAN4PR	EVOLUTION NitrX FEM CS/CR NONPOR TiNbN COATED SZ 4 RIGHT
EFSAN5PR	EVOLUTION NitrX FEM CS/CR NONPOR TiNbN COATED SZ 5 RIGHT
EFSAN6PR	EVOLUTION NitrX FEM CS/CR NONPOR TiNbN COATED SZ 6 RIGHT
EFSAN7PR	EVOLUTION NitrX FEM CS/CR NONPOR TiNbN COATED SZ 7 RIGHT
EFSAN8PR	EVOLUTION NitrX FEM CS/CR NONPOR TiNbN COATED SZ 8 RIGHT
Tibial Bases	
ETAKN1SL	EVOLUTION NitrX TIB KEELED NONPOR TiNbN COATED SZ 1 STD LEFT
ETAKN2SL	EVOLUTION NitrX TIB KEELED NONPOR TiNbN COATED SZ 2 STD LEFT
ETAKN3SL	EVOLUTION NitrX TIB KEELED NONPOR TiNbN COATED SZ 3 STD LEFT
ETAKN4SL	EVOLUTION NitrX TIB KEELED NONPOR TiNbN COATED SZ 4 STD LEFT
ETAKN5SL	EVOLUTION NitrX TIB KEELED NONPOR TiNbN COATED SZ 5 STD LEFT
ETAKN6SL	EVOLUTION NitrX TIB KEELED NONPOR TiNbN COATED SZ 6 STD LEFT
ETAKN7SL	EVOLUTION NitrX TIB KEELED NONPOR TiNbN COATED SZ 7 STD LEFT
ETAKN8SL	EVOLUTION NitrX TIB KEELED NONPOR TiNbN COATED SZ 8 STD LEFT
ETAKN1SR	EVOLUTION NitrX TIB KEELED NONPOR TiNbN COATED SZ 1 STD RIGHT
ETAKN2SR	EVOLUTION NitrX TIB KEELED NONPOR TiNbN COATED SZ 2 STD RIGHT
ETAKN3SR	EVOLUTION NitrX TIB KEELED NONPOR TiNbN COATED SZ 3 STD RIGHT
ETAKN4SR	EVOLUTION NitrX TIB KEELED NONPOR TiNbN COATED SZ 4 STD RIGHT
ETAKN5SR	EVOLUTION NitrX TIB KEELED NONPOR TiNbN COATED SZ 5 STD RIGHT
ETAKN6SR	EVOLUTION NitrX TIB KEELED NONPOR TiNbN COATED SZ 6 STD RIGHT

ETAKN7SR	EVOLUTION NitrX TIB KEELED NONPOR TiNbN COATED SZ 7 STD RIGHT
ETAKN8SR	EVOLUTION NitrX TIB KEELED NONPOR TiNbN COATED SZ 8 STD RIGHT
ETAKN2PL	EVOLUTION NitrX TIB KEELED NONPOR TiNbN COATED SZ 2 PLUS LEFT
ETAKN6PL	EVOLUTION NitrX TIB KEELED NONPOR TiNbN COATED SZ 6 PLUS LEFT
ETAKN8PL	EVOLUTION NitrX TIB KEELED NONPOR TiNbN COATED SZ 8 PLUS LEFT
ETAKN2PR	EVOLUTION NitrX TIB KEELED NONPOR TiNbN COATED SZ 2 PLUS RIGHT
ETAKN6PR	EVOLUTION NitrX TIB KEELED NONPOR TiNbN COATED SZ 6 PLUS RIGHT
ETAKN8PR	EVOLUTION NitrX TIB KEELED NONPOR TiNbN COATED SZ 8 PLUS RIGHT
